4.2.4. Accumulation Ratio (Part 2A Repeat Dose)

The extent of accumulation after repeat dosing will be determined via computation of accumulation ratios based on AUC_τ (R_{AUC}), on C_{\max} ($R_{C_{\max}}$) and on C_τ (R_{C_τ}).

Also, accumulation ratios would be estimated and reported by analysing the \log_e transformed AUC_τ , C_{\max} and C_τ using Mixed Model with the following effects:

- Fixed effect: Day, dose, day*dose
- Random effect: Subject

An unstructured covariance matrix will be considered for the G matrix describing the between subject variability. If this model fails to converge, alternative covariance structures may be considered such as Variance Component, Compound Symmetry, etc. Akaike's Information Criteria (AIC) will be used to assist with the selection of covariance structure.

The Kenwood and Roger method for approximating the denominator degrees of freedom and correcting for bias in the estimated variance-covariance of the fixed effects will be used.

CCI in cohorts 3, 4 and 5 will be compared with Day 1 to estimate the accumulation ratio. Point estimates and 90% CIs for the geometric mean ratio for “CCI/Day 1” will be constructed.

4.2.5. Steady State Analysis (Part 2A Repeat Dose)

An assessment of time to achieve steady state will be made based on visual inspection, by plotting trough concentration levels, C_{τ} , collected pre-dose (on CCI versus collection day by dose.

Only if required steady state will be assessed separately for each dose by analysing \log_e transformed trough plasma concentration (C_{τ}) using Mixed Model with the following effects:

- Fixed effect: Day
- Random effect: Subject

An unstructured covariance matrix will be considered for the G matrix describing the between subject variability. If this model fails to converge, alternative covariance structures may be considered such as Variance Component, Compound Symmetry, etc. Akaike's Information Criteria (AIC) will be used to assist with the selection of covariance structure.

The Kenwood and Roger method for approximating the denominator degrees of freedom and correcting for bias in the estimated variance-covariance of the fixed effects will be used.

Distributional assumptions underlying the model used for analysis will be examined by obtaining a normal probability plot of the residuals and a plot of the residuals versus the fitted values (i.e., checking the normality assumption and constant variance assumption of the model respectively) to gain confidence that the model assumptions are reasonable.

The coefficients of the slopes for the day (on CCI effect on log scale for each dose, along with 90% CI, will be used to determine whether steady state was achieved.

4.3. Secondary Endpoint Analyses

To investigate the effect of food on PK characteristics of single dose GSK3965193 tablets (Part 2B).

4.3.1. Endpoints

$AUC_{(0-inf)}$, C_{max} and T_{max} at fed and fasted condition

4.3.1.1. Main Analytical approach

An assessment of food effect will be based on \log_e transformed $AUC_{(0-\text{inf})}$, C_{max} with fasted Dose 1 of the tablet formulation of GSK3965193 versus \log_e transformed $AUC_{(0-\text{inf})}$, C_{max} with fed Dose 1 of the tablet formulation of GSK3965193. Statistical analysis will be based on Mixed Model with following effects:

- Fixed effect: treatment (Fed GSK3965193 dose 1 of Tablet and Fasted GSK3965193 dose 1 of Tablet), period
- Random effect: Subject

An unstructured covariance matrix will be considered for the G matrix describing the between subject variability. If this model fails to converge, alternative covariance structures may be considered such as Variance Component, Compound Symmetry, etc. Akaike's Information Criteria (AIC) will be used to assist with the selection of covariance structure.

The Kenwood and Roger method for approximating the denominator degrees of freedom and correcting for bias in the estimated variance-covariance of the fixed effects will be used.

Distributional assumptions underlying the model used for analysis will be examined by obtaining a normal probability plot of the residuals and a plot of the residuals versus the fitted values (i.e., checking the normality assumption and constant variance assumption of the model respectively) to gain confidence that the model assumptions are reasonable.

The estimated geometric mean ratios and 90% CI for (Fed GSK3965193 dose 1 of Tablet formulation: Fasted GSK3965193 dose 1 of Tablet formulation) will be derived.

T_{max} will be analysed non parametrically applying a Wilcoxon signed rank test and a point estimate and distribution free 90% CI for the median difference in T_{max} for (Fed vs Fasted) will be derived. This analysis will be used to derive point estimate and distribution free 90% CI for the median difference of (Fed vs Fasted).

If data permits, Fasted GSK3965193 Tablet formulation will be compared with Fasted GSK3965193 Solution formulation of same strengths.

4.4. Safety Analyses

The co-primary objective of this study is to assess the safety and tolerability of single and repeat ascending doses in healthy participants.

The safety analyses will be based on the safety population, unless otherwise specified.

Estimand for Safety Analyses:

Refer to Section [1.1.2](#).

4.4.1. Extent of Exposure

The extent of exposure will be summarised using GSK Core Data Standards. Further details of the planned displays will be given in the OPS.

Number of days of exposure to study drug will be calculated based on the formula:

- Duration of Exposure in Days = Treatment Stop Date – (Treatment Start Date) + 1

Subjects who were randomized but did not report a treatment start date (i.e., were randomized in error) will be categorised as having zero days of exposure.

The cumulative dose will be based on the formula:

- Cumulative Dose = Sum of (Number of Dosing Days x Total Daily Dose)

Duration of exposure and cumulative dose will be calculated only for Part 2A for cohorts 3, 4 and 5.

4.4.2. Adverse Events

An adverse event (AE) is considered study intervention emergent if the AE onset date is on or after study intervention start date. This definition of study intervention emergent AE is applicable only for Part 2A.

For Part 1 and Part 2B, an AE is considered study intervention emergent if the AE onset date is on or after study intervention start date (i.e., Day 1) till CCI after study intervention administration. Any AE which starts post Day 5 of study intervention administration will not be considered as study intervention emergent AE.

All AE summaries will be based on study intervention emergent events unless otherwise specified. SAE summaries will be based on all SAEs reported regardless of whether they meet the definition of study intervention emergent or not.

Adverse event (AE) will be coded using Medical Dictionary for Regulatory Activities (MedDRA) central coding dictionary. Adverse event analysis will be based on GSK Core Data Standards.

The following displays for Adverse events will be generated: All Adverse Events by System Organ Class and Preferred Term, AEs leading to withdrawal, Adverse Event by maximum severity grade, Treatment related Adverse Events, Treatment related AEs leading to withdrawal, Treatment relates AEs leading to death, Serious and non-serious Adverse Events and Serious Adverse Events. Further details of the planned displays will be given in OPS.

4.4.2.1. Adverse Events of Special Interest

No AEs of special interest will be collected in Part 1 and Part 2.

4.4.2.2. COVID-19 Assessment and COVID-19 AEs

A standardized MedDRA Query (SMQ) will be used to identify all COVID-19 – related AEs.

Recommended COVID-19 displays as per GSK Core Standards will be reported. If required some additional (optional) COVID displays would be reported if there is any impact observed on the study.

4.4.3. Additional Safety Assessments

4.4.3.1. Laboratory Data

Laboratory evaluations including the analyses of Chemistry laboratory tests, haematology laboratory tests and Urinalysis, will be based on GSK Core Data Standards for Parts 1 and 2.

Laboratory parameters will be graded using DAIDs grading. Division of AIDS (DAIDS) for Grading Division of AIDS for Grading the Severity of Adult and Paediatric Adverse Events Version 2.0.

Summary statistics for change from baseline will be tabulated. Worst-case chemistry parameters will be summarised by toxicity grades (DAIDS). Laboratory evaluations will be based on GSK Core Data Standards. The details of the planned displays will be given in the OPS.

Incidence of clinically significant laboratory parameters will be reported. Refer the normal ranges of laboratory parameters in the Section [6.2.1](#).

4.4.3.2. Vital Signs

The analyses of vital signs will be based on GSK Core Data Standards, unless otherwise specified.

In vital sign assessment, pulse rate, respiratory rate and blood pressure will be assessed. Blood pressure and pulse measurement will be taken in the semi supine position.

Post dose vital sign measurements will be captured at Day 1 (0.5 hour, 1, 4, 12) and Day 2 (24 hour of Day 1) for Part 1 and Part 2B.

Vital sign will be captured pre-dose daily for Part 2A.

Incidence of clinically significant vital sign parameters will be reported. Refer the normal ranges of laboratory parameters in the Section [6.2.1](#).

Further details of the planned displays will be given in OPS.

4.4.3.3. ECG

The analysis of 12-lead ECG along with any ECG findings will be reported according to GSK Core Data Standards.

Safety ECGs will be performed in semi-supine position after at least 5 minutes rest. The parameters collected are PR, QRS, QT and QTc intervals.

Incidence of clinically significant ECG parameters will be reported. Refer the normal ranges of laboratory parameters in the Section [6.2.1](#).

Further details of the planned displays will be given in OPS.

4.4.3.4. Sensory Nerve Conduction Testing

The analyses of sensory nerve conduction testing will be based on GSK Core Data Standards, unless otherwise specified.

Sensory Nerve conduction testing will be performed to ascertain Nerve conduction velocity (NCV) and Nerve conduction amplitude in Part 2A. Summary statistics of actual and change from baseline by day **CCI** in NCV and NCA will be provided.

Frequency and percentages of participants having 25% decrease in NCV and 50% decrease in nerve conduction amplitude from baseline will be reported.

Section [6.2.1](#) for Toronto Clinical Neuropathy Scoring System.

Further details of the planned displays will be given in OPS.

4.4.3.5. Nerve Function Test using Toronto Clinical Neuropathy Scoring System (TCNS)

Clinical nerve function testing will be conducted using TCNS. Summary statistics of actual and change from baseline by days **CCI** in nerve function test will be reported.

Incidents of participants having a total score > 4 or an increase from baseline ≥ 2 -point will be reported.

CCI **CCI**

CCI **CCI**

CCI

CCI

CCI

CCI [REDACTED]
 CCI [REDACTED]
 CCI [REDACTED]
 CCI [REDACTED]
 CCI [REDACTED]
 CCI [REDACTED]
 CCI [REDACTED]
 CCI [REDACTED]
 CCI [REDACTED]
 CCI [REDACTED]
 CCI [REDACTED]

4.6. Dose Escalation (For Part 1 and Part 2A)

Dose escalation for Part 1 and 2A will be based on predictive probability of any participant exceeding PK threshold at the next dose.

At each dose (Dose 2 onwards for Part 1 cohort 1), the Bayesian predictive probability of an individual exceeding the No Adverse Effect Limit (NOAEL) C_{\max} and $AUC_{(0-\infty)}$ threshold in Part 1 and No effect Nerve Conduction Velocity (NCV) $AUC_{(0-24)}$ in Part 2A will be calculated and compared with 50% probability threshold. This will be used to help selection of next dose together with safety and tolerability data. The Bayesian predictive probability will be based on Whitehead's model shown below [Whitehead,2001] using non-informative prior for model parameters.

$$y_{ij} = \theta_1 + \theta_2 d_{ij} + s_i + \varepsilon_{ij} \quad [1]$$

Where y_i is log-PK parameter of i-th participant, d_i is the log-dose administered to i-th participant, s_i is the random effect of the i-th participant. θ_1 and θ_2 are population intercept and slope, respectively and ε_i is random error of i-th participant in j-th dose.

If intra-subject variability cannot be estimated during PK predictions in Part 1 (i.e., early in the study when there is not sufficient information to estimate intra-participant variability) and for conducting prediction for all doses in Part 2A, the same Whitehead's model, will be used for Bayesian predictive probability calculations as below.

$$y_i = \theta_1 + \theta_2 d_i + \varepsilon_i \quad [2]$$

Where y_i is log-PK parameter of i-th participant, d_i is the log-dose administered to i-th participant. θ_1 and θ_2 are population intercept and slope, respectively and ε_i is random error of i-th participant in j-th dose.

MCMC procedure will be used to obtain the estimated parameters θ_1 , θ_2 , s_i ($i=1,2,3,4,5,6$) and σ^2 .

To obtain predicted PK exposure at next dose from the posterior predictive distribution $N(\theta_1 + \theta_2 \cdot \text{next dose} + s_i, \sigma^2)$ for each participant, $i=1,2,3,4,5,6$; 20000 iterations need to run.

N, i.e., number of iterations need to be counted to obtain at least one participant among 6 participants having exposure exceeding the C_{\max} threshold at next dose. $N/20000$ is the probability $p1 = \text{Prob}(\text{any participant's } C_{\max} \text{ at next dose level} > C_{\max} \text{ threshold})$.

In similar way, $p2 = \text{Prob}(\text{any participant's } AUC_{(0-\text{inf})} \text{ at next dose level} > AUC_{(0-\text{inf})} \text{ threshold})$ will be calculated.

If both probabilities $p1$ and $p2$ are less than the 50% threshold, then escalate to the next dose level.

4.7. Interim Analyses

Part 1 cohorts 1 and 2 data will be analysed and reported at the end of Part 1 cohort 2 completion.

Part 2 cohorts 3, 4 and 5 (Part 2A) and 6 (Part 2B) data will be analysed and reported at the end of Part 2B cohort 6 completion.

Also, preliminary safety data and PK data will be reviewed in-stream by the dose escalation committee prior to each dose escalation between cohorts in both Parts, 1 and 2A.

4.8. Changes to Protocol Defined Analyses

Details of changes or deviations to the originally planned statistical analysis specified in the Protocol Version 1.0 (Dated: 26-Jan-2022) are documented in [Table 2](#)

Table 2 Changes from the Planned Analysis

Protocol Defined Analysis	SAP defined Analysis	Rationale for Changes
Analysis Sets: “All Screened Subjects” and “Randomized Set” were not defined in the protocol.	Analysis Sets: Two additional analysis sets defined for Part 1 and 2. These are “All Screened Subjects” and “Randomized Set”	OPS requirement to display number of screen failures and screen failure reasons.
Interim Analysis: Interim reporting for Part 1 at the end of Part 1 cohort 2 was not planned.	Interim Analysis: Interim reporting for Part 1 at the end of Part 1 cohort 2 is planned now.	To plan for Part 3, study team decided to analyse and report the data for Part 1 separately at the end of Part 1.

5. SAMPLE SIZE DETERMINATION

CCI

CCI

6. SUPPORTING DOCUMENTATION

6.1. Appendix 1 Study Population Analyses

A summary of the number of participants in each of the participant level analysis sets will be provided for the Screened analysis set.

The Safety Analysis Set will be used for all other study population analyses unless otherwise specified. Please refer Section 3 for more information on the analysis sets.

Study population analyses including analyses of subject's disposition, protocol deviations, demographic and baseline characteristics, medical history, prior or concomitant medications and exposure will be based on GSK Core Data Standards. Detailed of the planned displays will be given in the OPS.

6.1.1. Participant Disposition

A summary of the number and percentages of subjects who completed the study as well as those who prematurely withdrew from the study will be provided. Reason for study withdrawal will be summarised. A subject is considered to have completed the study if they have completed study assessment till the end of the study as per the schedule of assessments, including the follow-up visit.

A summary of study intervention status will be provided. This display will show the number and percentage of subjects who have completed the scheduled study intervention, are ongoing with study intervention, or have discontinued study intervention prematurely, as well as primary reasons for discontinuation of study intervention. A summary of the number of subjects in each of the analysis sets described in the Section 3 will be provided.

All the data will be summarized based on GSK Core Data Standards.

6.1.2. Demographic and Baseline Characteristics

The demographic characteristics including age, gender, ethnicity, race, height/weight at screening and Body Mass Index (BMI) will be summarized using descriptive statistics.

Past medical conditions and current medical conditions as of screening will be summarized respectively. Medical history, vaccination, substance use, including smoking history, , alcohol and drug history will be summarized.

All the data will be summarized based on GSK Core Data Standards.

6.1.3. Protocol Deviations

Important protocol deviations will be summarized.

Protocol deviations will be tracked by the study team throughout the conduct of the study. These protocol deviations will be reviewed to identify those considered as important as follows:

- Data will be reviewed prior to freezing the database to ensure all important deviations (where possible without knowing the study intervention details) are captured and categorised in the protocol deviations dataset.
- This dataset will be the basis for the summaries of important protocol deviations.

6.1.4. Prior and Concomitant Medications

Concomitant medications will be coded using WHO Drug Dictionary. Summary will also be based on WHO Drug dictionary. The summary of concomitant medications will be provided by ingredient, i.e., multi-ingredient medications will be summarized for each individual ingredient rather than a combination of ingredients. The summary will be created using ingredient base names, i.e., ingredients with the same base name but different salt will appear under one base name in the summary. Anatomical Therapeutic Chemical (ATC) classifications will not appear in the summary.

Concomitant medications include any medication that was taken at some point during the on-intervention period as defined in Section [6.2.2](#)

6.2. Appendix 2 Data Derivations Rule

6.2.1. Criteria for Potential Clinical Importance

A laboratory value that is outside the reference range is considered either high abnormal (value above the upper limit of the reference range) or low abnormal (value below the lower limit of the reference range). Note: a high abnormal or low abnormal laboratory value is not necessarily of clinical concern.

Any additional laboratory parameters reported in the raw dataset for which no PCI ranges are provided in the following table will be listed.

Criteria specified below will be used to flag for potential clinical importance:

Analyte	Gender	Age range	Reference range	Units
Haematology				
HAEMOGLOBIN	Female	18-55yrs	115 - 155	g/L
	Male		130 - 170	g/L
HCT	Female		33 - 45	%
	Male		37 - 50	%
RED CELL COUNT	Female		3.95 - 5.15	$\times 10^{12}/L$
	Male		4.40 - 5.80	$\times 10^{12}/L$
MCV	Male/Female	18-55yrs	80 - 99	fL
MCH	Male/Female		26.0 - 33.5	pg
PLATELET COUNT	Male/Female		150 - 400	$\times 10^9/L$
WHITE CELL COUNT	Male/Female		3.0 - 10.0	$\times 10^9/L$
NEUTROPHILS	Male/Female		2.0 - 7.5	$\times 10^9/L$
LYMPHOCYTES	Male/Female		1.2 - 3.65	$\times 10^9/L$
MONOCYTES	Male/Female		0.2 - 1.0	$\times 10^9/L$

Analyte	Gender	Age range	Reference range	Units
EOSINOPHILS	Male/Female		0.0 - 0.4	x10 ⁹ /L
BASOPHILS	Male/Female		0.0 - 0.1	x10 ⁹ /L
PROTHROMBIN TIME	Male/Female		10 - 12	secs
INR	Male/Female		0.9 - 1.2	
APTT	Male/Female		25 - 37	Secs
ANTINUCLEAR ANTIBODIES	Male/Female		NEGATIVE	
SMOOTH MUSCLE ANTIBODIES	Male/Female		NEGATIVE	
CYTOMEGALOVIRUS AB (IGM)	Male/Female		NEGATIVE	
EPSTEIN-BARR VIRUS SCREEN	Male/Female		NEGATIVE	
EBNA IGG ANTIBODY	Male/Female	18-55yrs	(< 5 U/ml Negative)	U/mL
EBV EARLY AG AB. (IGG)	Male/Female		(<10 U/ml Negative)	U/mL
EBV VCA AB. (IGM)	Male/Female		(<20 U/ml Negative)	U/mL
DOUBLE STRANDED DNA ANTIBODY	Male/Female		<10 is Negative	IU/mL
SARS-COV-2 PCR	Male/Female		Not detected	
HEPATITIS B DNA	Male/Female		Not detected	
WBCS	Male/Female		0 - 52	cells/uL
RBCS	Male/Female		0 - 52	cells/uL

Analyte	Gender	Age range	Reference range	Units
HYALINE CASTS	Male/Female		Not seen	HPF
GRANULAR CASTS	Male/Female		Not seen	HPF
CELLULAR CASTS	Male/Female		Not seen	HPF
HEPATITIS B SURFACE ANTIGENS (HBSAG)	Male/Female		NEGATIVE	
HEPATITIS E AB - IGM	Male/Female		NEGATIVE	
CRYOGLOBULINS	Male/Female		Negative	
ALKALINE PHOSPHATASE ISOENZYMES	Male/Female		Negative	
Chemical Chemistry				
SODIUM	Male/Female	18-55yrs	135 - 145	mmol/L
POTASSIUM	Male/Female		3.5 - 5.1	mmol/L
CHLORIDE	Male/Female		98 - 107	mmol/L
UREA	Male/Female		1.7 - 8.3	mmol/L
BLOOD UREA NITROGEN	Male/Female		4.76 - 23.24	mg/dL
CREATININE	Female		49 - 92	umol/L
	Male		66 - 112	umol/L
BILIRUBIN	Male/Female		0 - 20	umol/L
DIRECT (CONJ) BILIRUBIN	Male/Female		0 - 5	umol/L
INDIRECT BILIRUBIN	Male/Female		<15	umol/l
ASPARTATE TRANSFERASE	Female		0 - 31	IU/L
	Male		0 - 37	IU/L
LDH	Female		135 - 214	IU/L
	Male		135 - 225	IU/L
TOTAL PROTEIN	Male/Female		63 - 83	g/L
ALBUMIN	Male/Female		34 - 50	g/L
CALCIUM	Male/Female		2.20 - 2.60	mmol/L

Analyte	Gender	Age range	Reference range	Units
RANDOM BLOOD GLUCOSE (SST)	Male/Female		3.5 - 7.9	mmol/L
C3	Male/Female		0.90-1.80	g/L
C4	Male/Female		0.10-0.40	g/L
COMPLEMENT C5A	Male/Female		13-179	ng/ml
COMPLEMENT BB	Male/Female		0.80-6.26	ug/ml
HEPATITIS D ANTIBODY	Male/Female		Negative	
HEPATITIS B 'E' ANTIGEN	Male/Female	18-55yrs	Negative	
SERUM ACETAMINOPHEN	Male/Female		10-30	

ECG Parameter Ranges:

ECG Parameters	Unit	Clinical Concern Range	
		Lower(<x)	Upper(>x)
Absolute QTc	msec	300	600
Absolute QTcF	msec	300	450
Uncorrected QT	msec	N/A	600
Heart rate	bpm	40	110
Absolute QRS interval	msec	70	120
Absolute PR Interval	msec	90	220
Change from Baseline:			
QTcF	msec	>60	

Vital Sign:

Vital Parameters	Unit	Clinical Concern Range	
		Lower(<x)	Upper(>x)
Pulse rate	bpm	40	110
Respiratory Rate	Breaths/min	8	20
Systolic blood pressure	mmHg	85	160
Diastolic Blood Pressure	mmHg	45	100

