### 7.1.2. QTc Stopping Criteria

If a clinically significant finding is identified including, but not limited to changes from baseline in QTcF after enrolment, the investigator or qualified designee will determine if the participant can continue in the study and if any change in participant management is needed. This review of the ECG printed at the time of collection must be documented. Any new clinically relevant finding should be reported as an AE.

The QTcF correction formula must be used for each participant to determine eligibility for and discontinuation from the study. This formula may not be changed or substituted once the participant has been enrolled. If an ECG demonstrates a prolonged QT interval, two more ECGs should be obtained over 5-10 mins and the average QTcF value of the three ECGs should be used to determine if the participant meets the QTc stopping criteria below.

A participant who meets the below QTc stopping criteria (based on the average of triplicate ECG readings) will be withdrawn from study intervention:

- QTcF >500 msec OR uncorrected QT >600 msec
- Change from baseline QTcF >60 msec

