6.2. Appendix 2 Data Derivations Rule

6.2.1. Criteria for Potential Clinical Importance

Laboratory test values will be considered of potential clinical importance if they fall outside the specified PCI ranges provided in the table compared to the baseline values.

Reference ranges for all laboratory parameters collected throughout the study are provided by the laboratory. A laboratory value that is outside the reference range is considered either high abnormal or low abnormal.

Grading categories for laboratory tests are determined using the [DAIDS, 2017] grading system Version 2.1.

Table 14 List of PCI Ranges for selected Laboratory Parameters

Analyte	Unit	PCI Range
ALT	IU/L	>2XULN
Albumin	g/dL	≤3.5
Glomerular filtration rate (GFR)	mL/min /1.73m ²	≤60
INR		>1.25
Platelet count	x 10 ⁹ /L	<140
Total bilirubin	umol/L	>1.25 x ULN

Table 15 List of PCI Ranges for ECG Parameters

ECG Parameters	Unit	PCI Range	
		Lower(<x)	Upper(>x)
Absolute QTc	msec	300	450
Absolute QTcF	msec	300	450
Uncorrected QT	msec	N/A	600
Heart rate	bpm	50	110
Absolute QRS interval	msec	70	120
Absolute PR Interval	msec	90	220
Change from Baseline:			
QTcF	msec	>60	

Table 16 List of PCI Ranges for Vital Sign Parameters

Vital Parameters	Unit	PCI Range	
		Lower(<x)	Upper(>x)
Pulse rate	bpm	50	110
Respiratory Rate	Breaths/min	8	20
Systolic blood pressure	mmHg	85	160
Diastolic Blood Pressure	mmHg	45	100

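### In the Parts 1 and 2 SAP the Absolute QTc reporting limit is 600 msec, the uncorrected-QT figure, so that row does not flag a QTc of 451 to 600 msec.

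*SAP*

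**What the plan says.** Section 6.2.1 of the Parts 1 and 2 SAP introduces its ranges with "Criteria specified below will be used to flag for potential clinical importance". In the ECG table a value counts as low if it is below the lower figure and high if it is above the upper figure. Three consecutive rows read:

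- "Absolute QTc msec 300 600"
- "Absolute QTcF msec 300 450"
- "Uncorrected QT msec N/A 600"

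A further row flags a QTcF change from baseline above 60 msec.

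Section 4.4.3.3 of the same SAP reports the incidence of clinically significant ECG parameters and points to Section 6.2.1 for the ranges. It states: "The parameters collected are PR, QRS, QT and QTc intervals". It does not name the correction formula. Section 1.1.1 lists that incidence within the primary safety endpoint for Parts 1 and 2.

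The other places that set a QT or QTc limit are:

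- Part 3 SAP, Section 6.2.1, Table 15: "Absolute QTc msec 300 450". The same table has 450 msec for QTcF and 600 msec for uncorrected QT.
- Protocol 5.2.1: healthy participants are excluded if QTc is above 450 msec. A note leaves the formula for data analysis to the analysis plan, and it may be QTcB, QTcF, another correction or a composite.
- Protocol 7.1.2: "QTcF >500 msec OR uncorrected QT >600 msec". The protocol attaches 600 msec to uncorrected QT only.

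**The concern.** The QTc row carries the same upper limit as the uncorrected-QT row two lines below it and differs from the QTcF row between them. A flag for potential clinical importance that starts only above 600 msec ignores values well above the 450 msec that the documents use elsewhere for a corrected QT.

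The row feeds a table that reports part of the primary safety endpoint of a first-time-in-human study. A reader who finds no QTc values of concern could take that as reassurance, when the limit applied was one meant for a different quantity.

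**Working it through.** No sample size, power or error rate is involved. The check applies each printed rule (flag if below the lower figure or above the upper figure) to the same values. Each column reads the value as if it were that column's quantity.

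| Value (msec) | Parts 1/2 QTc (<300 or >600) | Parts 1/2 QTcF (<300 or >450) | Parts 1/2 uncorrected QT (>600) | Part 3 QTc (<300 or >450) |
|---|---|---|---|---|
| 450 | no | no | no | no |
| 451 | no | flag | no | flag |
| 480 | no | flag | no | flag |
| 600 | no | flag | no | flag |
| 601 | flag | flag | flag | flag |

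**Width of the band.** 600 − 450 = 150 msec. In whole milliseconds this is 451 to 600, or 600 − 451 + 1 = 150 values. Triplicate means need not be whole numbers, so the exact band is above 450 and up to and including 600. At or below 450 and above 600 the two QTc limits agree.

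**What the band means depends on the correction, which the SAP does not name.**

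1. *QTc is QTcF.* The table then has two rows for one quantity. A value of 480 msec is flagged on the QTcF row and not on the QTc row. The incidence table would carry two different counts for the same measurement.
2. *QTc is another correction, for example QTcB.* The QTcF row does not apply to that quantity, the change-from-baseline row is also QTcF, and the uncorrected-QT row flags nothing up to 600 msec. A QTc of 451 to 600 msec by that correction is then flagged only if the QTcF of the same ECG also exceeds 450 msec, or its QTcF change exceeds 60 msec.

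The row is unsatisfactory on both readings.

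**Is the difference deliberate?** Between the two SAPs, the QTcF, uncorrected QT, QRS, PR and QTcF-change rows are identical. The version history of the Parts 1 and 2 SAP and its list of changes to protocol-defined analyses (Section 4.8) give no reason for 600 msec. Carry-over from the uncorrected-QT row is a reasonable inference that the documents do not confirm. The conflict between adjacent rows stands without it.

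**The case against.** The strongest reply is that the same table already covers the correction that matters. Protocol 7.1.2 requires QTcF for eligibility and discontinuation, protocol 8.2.3.1 defines a QTcF baseline, and the Parts 1 and 2 SAP flags QTcF above 450 msec and a change above 60 msec. No passage shows that a non-QTcF value was analysed. This stands, and it limits the impact to a QTc by another or unnamed correction, or to a contradictory duplicate row. It does not make the row right, because protocol 5.2.1 leaves other corrections open and the SAP does not choose.

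Protocol 7.1.2 also has new clinically relevant ECG findings reported as adverse events, and further ECG displays are left to the output specification, which is not available here. These are additional routes of capture, but they do not correct the printed limit.

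The comparison with Part 3 is weaker evidence than the conflict inside the table. The two SAPs also differ in the lower limit for heart rate and for pulse rate (40 against 50), so they were not meant to match row by row. Likewise, under protocol 7.1.2 the 450 msec exclusion is applied to QTcF, so it bears only indirectly on a QTc by another formula.

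Two stronger readings are tempting:

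- A reader might infer that participants at the QTcF withdrawal level go unreported. They do not: any QTcF above 500 msec is also above 450 msec and is flagged on the QTcF row. Setting a QTc of unnamed formula against a QTcF criterion mixes two quantities.
- A reader might infer that Parts 1 and 2 counts cannot be compared or combined with Part 3 counts. The documents describe no such pooling, and the populations differ (healthy participants, and participants with chronic hepatitis B).

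**Conclusion.** The point holds as a reporting error confined to one row. The Absolute QTc upper limit in the Parts 1 and 2 SAP is inconsistent with the adjacent QTcF row, with the QTc row of the Part 3 SAP and with the protocol's QTc exclusion figure. It leaves a 150 msec band unflagged on that row.

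The effect is on the descriptive incidence of clinically significant ECG values, within the primary safety endpoint. QTcF prolongation remains flagged, and withdrawal of participants follows protocol 7.1.2, not this table. No formal hypothesis is tested in these parts, so no inference is affected.

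Whether any reported count would change cannot be told from the documents. It depends on which correction was tabulated as QTc and on whether any value fell in the band.

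**What to change.** 1. State in the Parts 1 and 2 SAP which correction Absolute QTc means.
2. If it is QTcF, delete the row as a duplicate. If it is another correction, reconcile its reporting limit with the 450 msec in the adjacent row and in Part 3 Table 15, or justify a different figure.
3. Re-run the Parts 1 and 2 ECG incidence table with the reconciled row, or annotate the existing one.

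Protocol 9.5 says that Parts 1 and 2 have already been reported in full. The change is therefore a documented correction, and protocol Section 9 provides for it through a SAP addendum with a justification in the final study report. The cost is one table cell, one definition, one re-run or footnote, and that record. Nothing in the conduct of the trial changes.
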